7.3.1.4 DATA MANAGEMENT AND QUALITY CONTROL

Images are uploaded by site users to the Laboratory of Neuroimaging (LONI) at the University of Southern California. Data are deidentified as part of the upload and placed into quarantine until they pass quality assurance evaluation conducted by the PET Core. The aim of this work is not only to make sure that all PET scans are acquired and reconstructed using the appropriate protocols and

that image quality is good, but also to standardize the images from the different sites (and hence the different PET scanner vendors and models) as much as possible in order to reduce inter-site differences.

Quality control of scans could necessitate salvage with reprocessing of the raw imaging data. All sites are required to save original PET data for the duration of the study.

7.3.2 MRI

Participants will have a brain MRI scan as part of the screening evaluation, as well as at each ongoing in-clinic visit.

7.3.2.1 SITE QUALIFICATION

Each site must be qualified for MRI. The ADNI4 MRI protocol differs from that used in ADNI3 in that several of the sequences will be modernized. Therefore, all scanners will have to be qualified with the ADNI4 protocol MRI protocol.

The procedure for MRI site qualification will consist of a test imaging session on a human volunteer and/or phantom. If the scanner to be used in ADNI4 is currently qualified for ADNI3, then ADNI4 qualification only involves scanning a phantom (no human scan required). However, if the scanner in ADNI4 is not qualified for ADNI3 (i.e., a new scanner for the site's ADNI participants), then a human volunteer scan is needed for ADNI4 qualification. The site will be sent an electronic file containing the ADNI4 protocol that has been ported to the site's scanner make/model/operating system. The site will load the file onto the scanner to be qualified, and then image either a volunteer participant (typically a site staff member) or phantom with the protocol and send the images to LONI. The MRI Core will check each parameter in each of the pulse sequences in the protocol. If the scan has not been performed according to protocol, the site will be asked to perform another qualification scan. This will be repeated as many times as necessary until the site has demonstrated exact execution of the MR protocol in a volunteer participant (or phantom), at which point the scanner will be qualified for ADNI4. Human volunteers do not need to be elderly controls; in fact, scanning for site qualification may be more easily performed with normal younger volunteers. If repeat human volunteer attempts are needed, repeat scans need not be on the same volunteer participant. Once a site has demonstrated perfect execution of the protocol, the protocol will be stored permanently on the scanner at that site that will be used in the study.

7.3.2.2 DATA ACQUISITION

All participants will be scanned on a 3T MRI System with a protocol consisting of several sequences that conform to FDA safety standards. All sequences will be vendor product (FDA approved). The MRI protocol includes: a scout, structural T1-weighted MRI, FLAIR, T2 GRE, T2, diffusion tensor imaging, ASL perfusion MRI, and task free resting state functional MRI. The total scan time will be approximately one hour but may be slightly longer depending on technical factors. If the subject becomes uncomfortable, they can ask to be removed from the scanner at any time.

Each MRI scan of a participant's brain will be performed at Screening (for new participants), or Initial Visit (for rollover participants) and then again annually (or at every In-Clinic Visit).

7.3.2.3 CLINICAL READ OF MRIS

The research site is responsible to obtain a read from a local radiologist following local standards of care for each MRI completed in the ADNI protocol.

7.3.2.4 DATA MANAGEMENT AND QUALITY CONTROL

Images are uploaded by site users to the Laboratory of Neuroimaging (LONI) at the University of Southern California (USC). The MRI Core will perform a quality control review on each MRI scan. Quality control for MRI will result in failure of some scans, which may need to be repeated. Repeat scans must be scheduled as soon as possible and no later than four weeks of the visit date.

7.4 BIOSPECIMENS

Local labs, National Cell Repository for Alzheimer's Disease (NCRAD), and University of Pennsylvania (UPENN) will analyze all laboratory samples. Lab reports will be reviewed, signed and dated by the Site PI (or a medically-qualified individual delegated by the PI). Site clinicians will indicate whether abnormal lab results are clinically significant or not, with additional review by ATRI

Medical Monitoring group. Those results that are deemed clinically significant may need to be repeated and follow up with the participant's treating physicians will be recommended by study personnel.

7.4.1 **BLOOD DRAW**

The relevant study manual will provide detailed instructions for the collection, processing and shipment of all biofluid samples. Samples will be collected to accommodate the assay of the broadest range of the best antecedent biomarkers/analytes. Fasting overnight (minimum 6 hours) is required for plasma, serum and CSF sample collection. Only water is permitted (no food but water is encouraged) until blood draws and the LP procedure are completed. ADNI4 will continue to measure Aβ1-42, Aβ1-40, total tau, and phosphorylated tau181 in CSF samples.

Methods used for blood draw will continue as in ADNI3 for longitudinal biomarker and genetic data with the addition of PBMC collection.

7.4.1.1 BASELINE BLOOD SAMPLES FOR PBMC AND CELL LINE BANKING

Whole blood samples will be collected at baseline for all participants and used for extraction of peripheral blood mononuclear cells (PBMCs). For newly enrolled participants and rollovers who have not yet provided this sample, an additional blood sample will also be used to derive immortalized cell lines. Whole blood will be collected and shipped overnight under ambient conditions to NCRAD. It is important to ship samples drawn for PBMCs the same day they are drawn and that they are received at NCRAD the next day; any delay will affect the viability of the cells. The Genetics Core will request a re-sampling if the condition of the sample on arrival prevents processing.

PBMC has become an important source for the development of induced pluripotent stem cells (iPSCs) and also can support other functional genomic studies. Some cells may be derived into new materials. Processing may be performed at other laboratories in which case aliquots of the derived materials will be returned to NCRAD for distribution to NIA approved investigators.

Longitudinal Blood Samples for Genomic Analysis and Related Bioassays 7.4.1.1.1

At baseline and follow-up visits, blood will be collected for extraction of DNA and RNA at NCRAD and to provide plasma and serum for the Biomarker Core. Whole blood is processed at each site to separate plasma, serum, buffy coat (white blood cells), and red blood cell (RBC) components. The buffy coat and RBC components are aliquoted at the sites and shipped overnight under ambient conditions to NCRAD where DNA will be extracted, aliquoted and banked. RBCs will be banked for specialized assays requiring RBCs. RNA samples will also be collected at each visit using Paxgene kits supplied by the ATRI Coordinating Center. Paxgene samples will be shipped overnight under ambient conditions to NCRAD and RNA will be extracted, aliquoted and banked. The longitudinal genomic sample collection will be used to analyze changes in gene transcription (RNA analysis) and epigenetic processes (e.g., DNA methylation, histone modification, and chromatin remodeling) and to enable future genomic analyses.

7.4.1.1.2 Genetic and Genomic Analyses

APOE and genome-wide genotyping will be completed for newly enrolled participants. For participants whose samples have not already undergone whole genome sequencing, resources will be sought during ADNI4 to perform these analyses.

7.4.1.1.3 Plasma and Serum Collection for Biomarkers

Plasma, serum, and buffy coat will be collected at Baseline from newly enrolled participants, and at the initial ADNI4 visit from rollover participants, and then ongoing during follow-up at In-Clinic Visits for all participants. All samples will be collected in the morning before breakfast and after an overnight fast (minimum 6 hour fast). Plasma and serum must be prepared at the site, frozen and then sent overnight on dry ice to the Biomarker Core at the UPENN. As above, buffy coat and red blood cells will be extracted from blood at the site and shipped overnight under ambient conditions to NCRAD.

LUMBAR PUNCTURE 7.4.2

The Lumbar Puncture procedure is optional for all participants. Should a newly enrolled or rollover participant agree to the optional LP, they will have CSF samples collected at Baseline and again every 2 years through the course of the ADNI4 study. All samples will be collected in the morning before breakfast and after an overnight fast (minimum 6 hours fast).

Approximately, 2 ml of CSF should be sent to the clinical laboratory of the Site PI for routine cell count, protein and glucose analyses. The majority of the CSF, at least 20 ml should be immediately frozen and sent overnight frozen on dry ice directly to the ADNI Biomarker Core laboratory for processing and storage in the ADNI Fluid Bank at UPENN.

Each study participant or a person designated to speak on their behalf will be contacted by phone 24 hours after the lumbar puncture to confirm the participant's well-being and to query about any new adverse events.

At the discretion of the Site PI (or Site Clinician), a coagulation panel (PT/PTT) may be obtained to rule out a clotting disorder. Also, per PI (or Site Clinician) discretion, anti-platelet agents (e.g., aspirin) may be discontinued for a period of time before and after the LP.

7.4.3 NEUROPATHOLOGY

Participants at all sites will be approached to register in ADNI's brain donation program. At the time of death, a participant's next of kin may be asked to agree to a brain-only autopsy. Participants are encouraged to discuss their wishes with family members in advance of their passing. The participants/families will be approached by an investigator at an appropriate time to discuss registration in the brain donation/autopsy program. Interested participants/study partners will be given informational, site-specific materials about the brain donation program and whom to contact at their site at the time of death. A protocol is contained within the relevant study manual for the processing of brain tissue from all participants that come to autopsy, provision of the tissue to the Neuropathology Core, and documentation required that accompany that tissue. Participants enrolled in other studies may still register for ADNI's brain donation program. The Neuropathology Core will make arrangements with the other study for tissue sharing.

7.5 ADVERSE EVENTS AND SERIOUS ADVERSE EVENTS FOR IN-CLINIC COHORT

7.5.1 ADVERSE EVENT (AE) DEFINITION

An Adverse Event (AE) is any untoward medical occurrence including adverse change from the participant's baseline condition, including clinical or laboratory tests, or abnormalities that occur during the course of the study after consent.

All AEs are to be documented, regardless of relationship to study procedures, commercial, or investigational products used in this study (amyloid (Florbetapir, Florbetaben, NAV4694) or tau (Flortaucipir, MK6240, PI2620) PET tracers), beginning from the time the participant signs the Informed Consent Form (ICF) through the last study visit or last assessment.

All research team members will be participating in ensuring subject safety. All participants will be evaluated for adverse events at each visit.

The investigator is obliged to follow participants with AE's until the events have subsided, the conditions are considered medically stable, or the participants are no longer available for follow up. Participants who discontinue due to Adverse Events will be treated and followed according to established medical practice. All pertinent information will be entered into the eCRF.

AEs the site PI (or medically qualified designee) deems related to study procedures or investigational products used in this study and serious adverse events (SAEs) occurring within 24 hours of PET tracer administration, regardless of causality, are to be documented beginning from the time the participant signs the ICF through the last study visit or last assessment.

AE identification criteria and reporting requirements will be provided in the relevant study manual and must be followed regardless of applicable regulatory requirements that may be less stringent.

7.5.2 SERIOUS ADVERSE EVENT (SAE) DEFINITION

A serious adverse event (SAE) is defined as an adverse event or suspected adverse reaction that results in any of the following outcomes:

- death;
- a life-threatening adverse event (i.e., the participant was at immediate risk of death from the AE as it occurred; this does not include an event that, had it occurred in a more severe form or was allowed to continue, might have caused death);
- in-patient hospitalization (>24 hours) or prolongation of existing hospitalization including emergency room visits (see the relevant study manual for more information regarding hospitalizations);
- a persistent or significant disability/incapacity or substantial disruption of the ability to conduct normal life functions;
- or a congenital anomaly/birth defect

Important medical events that may not result in death, be life-threatening, or require hospitalization may be considered serious when, based upon appropriate medical judgment, they may jeopardize the participant or may require intervention to prevent one of the outcomes listed in the definition above. Examples of such medical events include allergic bronchospasm requiring intensive treatment in an emergency room or at home, blood dyscrasias or convulsions that do not result in inpatient hospitalization, or the development of drug dependency or drug abuse.

Upon notification of a participant's death, the Neuropathology Core will reach out to the next of kin and the site to request additional information regarding brain donation and autopsy.

For more information, refer to the Code of Federal Regulation Title 21 Part 312.

7.5.3 EVENT ASSESSMENT, REPORTING, AND FOLLOW-UP

The occurrence of an adverse event (AE) or serious adverse event (SAE) may come to the attention of clinical site personnel during study visits; as a result of laboratory report and/or imaging read findings; through other interactions with the participant, caregiver, and/or study partner/knowledgeable informant; or as a result of clinical monitor review of study records. Solicitation of specific events will not be required (i.e., the participant will not be asked if they have experienced any specific adverse events).

All AEs and SAEs will be captured on the CRF as described in Section 7.5 and in the relevant study manual. All AEs and SAEs that occur during study participation (i.e., after consent is signed and through the last study visit or assessment) must be documented, regardless of relationship to study procedures or investigational products used in this study (e.g.: PET tracers), and must be followed to adequate resolution.

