7.3.1.2 DATA ACQUISITION FOR PET SCANS

All ADNI participants will complete one amyloid PET scan and one tau PET scan every two years. Scans must be completed within 2 weeks before or 2 weeks after the in-clinic assessments at Initial/Baseline visit and at two-year intervals.

Individuals who are retained in ADNI4 from ADNI3 will continue to have amyloid PET scans with the ligand that was used in ADNI3 (either FBB or FBP) and will continue to have tau PET scans with the ligand that was used in ADNI3 (FTP). Participants that are newly recruited to ADNI4 will be assigned to tracers based on the clinical site proximity to PET tracer manufacturing sites. In ADNI4 because there are 3 possible amyloid tracers and 3 possible tau tracers, there are 9 possible combinations of tracers that new individuals will receive. Each participant will be assigned to one amyloid tracer and one tau tracer that is expected to remain stable for the duration of the study. In the United States, florbetapir, florbetaben and flortaucipir are all FDA approved tracers for PET imaging. NAV4694, MK6240, and PI2620 are not currently FDA approved and will be used under IND held by ATRI investigators. In Canada, only florbetaben is approved by Health Canada (HC) for PET imaging. Use of remaining tracers (florbetapir, flortaucipir, NAV4694, MK6240, and PI2620) will be submitted to HC by ATRI investigators for approval for use in the ADNI4 study.

Scan protocols differ for each tracer. The injected doses for each tracer are listed in the table to the right. After insertion of an intravenous line, tracer is injected outside the scanner. Following injection, participants remain in a comfortable state, usually in a chair but not in the scanner, for a period of time. Imaging times after injection are listed in the table for each tracer. Prior to each scan an x-ray CT (for PET/CT systems), or positron transmission scan (for PET-only systems) is obtained for attenuation correction of the image; an MRI scan (for PET/MRI systems) may be obtained before, after or during the PET scan. Technical details for scan acquisition will be provided in a technical manual and radiation dose exposure is provided in the technical manual. The total time commitment for a PET scan may range from about 1.5 hours to 2.5 hours.

Tracer	Injected Dose	Imaging Time (post-injection)
Florbetapir	10 mCi	50-70 min
Florbetaben	8.1 mCi	90-110 min
NAV4694	8.1 mCi	50-70 min
Flortaucipir	10 mCi	75-105 min
MK6240	5 mCi	90-110 min

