7.5.4 SERIOUS ADVERSE EVENT REPORTING AND FOLLOW-UP

Any such experience due to any cause, which occurs during the course of the investigation or within 30 days of the last study visit, must be reported to the ATRI Coordinating Center within 24 hours after learning of the event. This in turn will trigger an alert to the appropriate ATRI Coordinating Center personnel, which will lead to the initiation of the creation of a report. Sites will report SAEs based on the IRB/IEC and local institutional requirements.

A serious adverse event (SAE) reported to have occurred within 24 hours of amyloid (FBP, FBB, NAV4694) or tau (FTP, MK6240, PI2620) PET tracer administration will be reported, regardless of the investigator's opinion of causation. Thereafter, sites must continue to report any serious or life-threatening adverse event whether or not it is related to study procedures. A subset of those SAEs may then be reported to Avid, Life Molecular Imaging (LMI) and Cerveau for events related to florbetaben, florbetapir, NAV4694, flortaucipir, MK6240, PI2620.

All available information, including the site PI's assessment of causality, must be provided at the time the initial SAE is reported via the eCRF. The initial SAE report is to be followed as soon as possible by detailed descriptions including copies of hospital case reports, autopsy reports, and other documentation requested by the Data and Coordinating Center and/or the IRB/IEC.

Any relevant follow-up information received on SAEs should be reported within 24 hours of its receipt. If the relevant follow-up information changes the site PI's assessment of causality, this should also be noted on the follow-up SAE form.

The site PI is responsible to notify their IRB/IEC of the occurrence of the SAE in writing, if required by their institution. A copy of this communication must be forwarded to the Data and Coordinating Center, the IRB/IEC, or delegate(s) to be filed in the TMF.

The detailed contact information for reporting of SAEs is on the Study Contact Sheet made available to all sites.

For urgent safety issues, please ensure all appropriate medical care is administered to the participant and contact the appropriate study team member listed on the Study Contact Sheet.

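### AE and SAE documentation ends at the last visit or assessment, which conflicts with the protocol's own 24-hour and 30-day safety windows and leaves non-serious events after a final tracer injection without a documentation window

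*Protocol*

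**What the plan says.** Four sections of the protocol bear on when safety collection stops.

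- **Section 7.5.1** has all AEs documented "beginning from the time the participant signs the Informed Consent Form (ICF) through the last study visit or last assessment". A later paragraph says that SAEs "occurring within 24 hours of PET tracer administration, regardless of causality, are to be documented", and that sentence closes with the same end point.
- **Section 7.5.3** applies the end point to AEs and SAEs together: "after consent is signed and through the last study visit or assessment". No days are added.
- **Section 7.5.4** requires reporting of any serious event "which occurs during the course of the investigation or within 30 days of the last study visit". It repeats the 24-hour tracer rule without a cap at the last visit.
- **Section 7.4.2** requires a telephone call 24 hours after each lumbar puncture, partly "to query about any new adverse events".

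On timing, Section 7.3.1.2 states: "Scans must be completed within 2 weeks before or 2 weeks after the in-clinic assessments at Initial/Baseline visit", and applies this again at two-year intervals. The schedule in Section 1.3.1 (new participants) and Table 1.3.2.1 (rollovers without a full final ADNI3 visit) place amyloid PET, tau PET and the optional LP at Month 48. Section 7.1.7 asks for the same procedures, as far as possible, at an early-termination visit.

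**The concern.** An end point at the last visit or assessment works when that contact comes after the last exposure. Here the last assessment can itself be a tracer injection or an LP, so the window can close at the moment the final exposure begins to carry risk.

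Two things are at stake. First, sites cannot derive a single rule for SAEs after the last visit, because 7.5.3 and 7.5.4 give different end dates. Second, non-serious reactions to a final tracer injection are not required to be recorded. Three of the six tracers (NAV4694, MK6240 and PI2620) are used under IND according to Section 7.3.1.2. Section 7.5.5.2 asks the site to judge relatedness for exactly these three, partly on timing. A window that ends at the injection gives that judgement nothing to work on for the final dose.

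**Working it through.** The protocol states no figure to reproduce. The check compares the stated windows and then counts the exposures concerned.

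**Step 1. Coverage after a final exposure that is also the last assessment**

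| Event | Rule | Coverage |
|---|---|---|
| Non-serious AE after a final tracer injection | 7.5.1, 7.5.3 | 0 days, and no scheduled contact |
| New AE after a final LP | 7.5.1, 7.5.3 against 7.4.2 | Window 0 days, but an AE query at about 24 hours |
| SAE, documentation | 7.5.3 | 0 days |
| SAE, reporting | 7.5.4 | 30 days from the last visit |
| SAE within 24 hours of tracer | 7.5.1 | Capped at the last visit or assessment |
| SAE within 24 hours of tracer | 7.5.4 | Not capped |

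For SAEs the two end dates differ by 30 days. An SAE on day 10 after the last visit is reportable under 7.5.4 and, under Section 9.5, goes on both the SAE form and the AE pages of the CRF. It nevertheless lies outside the documentation period in 7.5.3.

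The 24-hour tracer period is not lost under 7.5.4. A scan 14 days after the clinic assessments puts its end at day 14 + 1 = 15, which is inside 30.

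**Step 2. Who can end on an exposure**

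- New CN and MCI participants, and CN and MCI rollovers in Table 1.3.2.1: PET and optional LP at Month 48, the last scheduled visit.
- Early-termination visits that include PET or LP.
- Not Table 1.3.3.1 rollovers who complete the schedule: PET and LP are at Months 12 and 36, and 48 - 36 = 12 months of contact follow.
- Not DEM participants who complete the schedule: telephone follow-up continues after Month 24.

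**Step 3. Size among new participants**

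Inputs: up to 750 new participants with target shares of 40% CN, 40% MCI and 20% DEM (Section 4.1.1.2), and two PET scans at each PET visit.

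- CN and MCI: 750 x 0.80 = 600 people. PET at Baseline, Month 24 and Month 48 gives 3 x 2 = 6 injections each, so 600 x 6 = 3,600.
- DEM: 750 x 0.20 = 150 people. PET at Baseline and Month 24 gives 2 x 2 = 4 injections each, so 150 x 4 = 600.
- Total: 3,600 + 600 = 4,200 scheduled injections.
- Only the last exposure per completer can have no window at all: at most 600 / 4,200 = 14.3%.

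This is a ceiling for the completed schedule. It assumes full enrolment, no attrition, no conversions, that everyone reaches Month 48 within the 5-year study, and that an injection is the last thing done. A scan done before the clinic assessments is followed by that visit's AE evaluation and is not affected. Rollovers and early-termination visits are not in the count, because the protocol does not give their numbers.

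**The case against.** The case on the other side is substantial, and much of it limits the point.

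- **A reader might infer that the last exposure has no safety follow-up.** The documents do not support that. Every LP has a 24-hour call, SAEs are reportable for 30 days after the last visit, and AEs already present are followed until they resolve or stabilise (7.5.1).
- **Section 7.5.3 says what must be documented and does not forbid recording more.** This stands. Sections 7.5.4 and 9.5 route reportable SAEs to the eCRF, so these SAEs need not be lost. What remains is two different end dates for the same class of event.
- **The post-LP call can be read as itself the last assessment.** That is a sensible reading, but the protocol does not state it.
- **A reader might infer that a late scan leaves only 30 - 14 = 16 days of SAE coverage.** That holds only if the scan lies outside the visit. Section 7.1.1 places imaging within the two weeks after a visit begins, so the 30 days may run from its completion. The anchor date is unclear rather than shown to be short.
- **A reader might count both Month 48 scans, 1,200 / 4,200 = 29%.** The earlier of the two scans still has a window running to the later one, so this overstates the gap.
- **A reader might infer biased per-exposure AE rates for the DSMB.** Section 9.5 describes SAE review and safety reports. No such rates or denominators are mentioned.
- **A later end date adds no contact after a final PET.** This is true. It makes events that are reported recordable, but does not ensure that they are heard of.
- **The study manual, not shown, carries AE reporting detail.** It may help sites, but the conflicting end dates are fixed in the protocol itself.

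**Conclusion.** The point holds in a limited form. The end of documentation in 7.5.1 and 7.5.3 contradicts the 30-day SAE period in 7.5.4, truncates the 24-hour tracer rule inside 7.5.1, and can exclude what the 24-hour LP call finds. The substantive gap is non-serious AEs starting after a final tracer injection, for participants whose last assessment is that scan.

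The 14% ceiling applies to new participants on the completed schedule, and the true share will be lower if participants drop out or have their scans before the clinic assessments. This is more than missing detail, because the stated rule itself leaves events outside its window and conflicts with other stated windows. It merits a correction, but it is not a failure of SAE surveillance.

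**What to change.** Reconcile Sections 7.4.2, 7.5.1, 7.5.3 and 7.5.4 into one stated end of AE and SAE documentation, counted from the later of the last visit and the last tracer administration or LP. That period should contain the windows the protocol already states: 24 hours after tracer, the 24-hour LP call, and 30 days for SAEs. Count the 30 days in 7.5.4 from the same date, which also settles whether a scan after the clinic assessments moves the anchor.

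The cost is a wording amendment and a change to the CRF end-date logic. The downside is that AE forms stay open slightly longer after the final procedure.
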